7.1 Objective Response Rate

The ORR is defined as the proportion of subjects whose best overall response is a confirmed CR or confirmed PR based on investigator assessment according to RECIST 1.1. The ORR will be estimated with a 95% CI using the exact probability method. The number and percent of subjects with the best overall response of CR, PR, SD, PD and not evaluable (NE) will be summarized.

Summary of objective response will be provided for the All Treated population and Response Evaluable population, respectively.

The best overall response based on RECIST 1.1 is defined as the best overall response among all post-baseline time point assessments until the first PD per RECIST 1.1 or start of new anti-cancer therapy, whichever is earlier. For subjects who have not met the criteria for PD per RECIST1.1 or have not started a new anti-cancer therapy, the best overall response is defined as the best overall response among all post-baseline timepoint assessments.

Based on the investigator assessment of overall response per RECIST 1.1 at post-baseline assessments, the best overall response will be determined programmatically as the following and Table 3:

- CR > PR > SD > PD > NE
- CR = at least two determinations of CR with at least 4 weeks apart before progression.
- PR = at least two determinations of PR or better with at least 4 weeks apart before progression (and not qualifying for CR).
- SD = at least one SD or better ≥ 49 days after the first dose and before progression (and not qualifying for a CR or PR). The minimum interval from the first dose date for the best response of SD is 8 weeks minus 7 days to allow for visit windows of ± 7 days (49 days).
- If the minimum interval for SD is not met, the best response will depend on the subsequent assessments. See table below for details.
- PD is considered the best overall response when PD is documented and a best overall response of CR, PR, or SD could not be established before documentation of PD. Clinical deterioration will not be considered as documented disease progression in the determination of the best overall response.
- NE is considered the best overall response when PD has not been documented and a best response of CR, PR or SD could not be established.

Table 3. Best overall response when confirmation of CR and PR required.

Overall response First time point	Overall response Subsequent time point	BEST overall response
CR	CR	CR
CR	PR	SD, PD or PR ^a
CR	SD	SD provided minimum criteria for SD duration met, otherwise, PD
CR	PD	SD provided minimum criteria for SD duration met, otherwise, PD
CR	NE	SD provided minimum criteria for SD duration met, otherwise, NE
PR	CR	PR
PR	PR	PR
PR	SD	SD, provided minimum criteria for SD duration met, otherwise, PD

Overall response First time point	Overall response Subsequent time point	BEST overall response
PR	PD	SD provided minimum criteria for SD duration met, otherwise, PD
PR	NE	SD provided minimum criteria for SD duration met, otherwise, NE
NE	NE	NE

CR = complete response, PR = partial response, SD = stable disease, PD = progressive disease,

Disease assessment at baseline including sum of target lesion diameters, number of target lesions, number of subjects with target lesions and non-target lesions will be summarized. The percent change from baseline in target lesion sum of diameters for all post-baseline disease assessments will be presented by subject using spider plot. The best percent change from baseline in target lesion sum of diameters is defined as the largest reduction or smallest increase (in the case where a reduction does not occur) from baseline observed over all post-baseline disease assessments up to and including the first PD and will be presented using a waterfall plot. Target lesion, non-target lesion, new lesion and response assessments will be presented in data listings. The percent change from baseline/nadir in target lesion sum of diameters will be displayed with 2 decimal places (xx.xx%) without rounding in the data listing.

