7.2 Clinical Benefit Rate

The CBR based on RECIST 1.1 is defined as the proportion of subjects whose best overall response is a confirmed CR, confirmed PR or SD \geq 16 weeks, where SD \geq 16 weeks is defined as at least one SD or better for \geq 15 weeks (16 weeks with 1 week visit window) and not qualifying for a confirmed CR or PR as the following:

Response at week 8 assessment	Response at week 16 assessment	Response at week 24 assessment	SD ≥ 16 weeks
SD	SD/PR/CR	Any	Yes
SD	PD	Any	No
SD	NE/missing	SD/PR/CR	Yes
SD	NE/missing	PD/NE/missing	No
CR/PR	PD	Any	No
PR	SD	Any	Yes
NE	SD	Any	Yes

The CBR will be estimated with a 95% CI using the exact probability method. Summary of CBR will be provided for the All Treated population and Response Evaluable population.

NE = not evaluable.

^a If a CR is truly met at first time point, then any disease seen at a subsequent time point, even disease meeting PR criteria relative to baseline, makes the disease PD at that point (since disease must have reappeared after CR). Best response would depend on whether minimum duration for SD was met. However, sometimes "CR" may be claimed when subsequent scans suggest small lesions were likely still present and in fact the patient had PR, not CR at the first time point. Under these circumstances, the original CR should be changed to PR and the best response is PR.

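### SAP 7.1 builds best overall response from bullets and Table 3 together, and the two conflict on recorded CR followed by PR and on early response followed by SD

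*SAP*

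**What the plan says.** SAP 7.1 defines ORR as the "proportion of subjects whose best overall response is a confirmed CR or confirmed PR based on investigator assessment according to RECIST 1.1". It then states that "the best overall response will be determined programmatically as the following and Table 3", so both sources feed one program.

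- **Bullets.** The categories are ranked "CR > PR > SD > PD > NE". The PR bullet is "PR = at least two determinations of PR or better with at least 4 weeks apart before progression (and not qualifying for CR". SD needs one assessment of SD or better at day 49 or later. On PD: "PD is considered the best overall response when PD is documented and a best overall response of CR, PR, or SD could not be established" up to that point. NE applies when PD has not been documented and nothing better can be established.
- **Table 3, CR then PR.** Three outcomes are listed (SD, PD or PR), with footnote a deciding. If the CR was real, later disease, "even disease meeting PR criteria relative to baseline, makes the disease PD at that point", and best response is SD or PD according to the SD minimum. If the CR was mis-called, it is to be changed to PR and best response is PR.
- **Table 3, CR then SD.** "SD provided minimum criteria for SD duration met, otherwise, PD". The PR-then-SD row is to the same effect.

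Table 3 handles pairs only, headed as a first and a subsequent time point. It has no three-visit rows.

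**The concern.** A programmed derivation needs one answer for each sequence of recorded responses. Here two stated rules can return different answers for the same subject, and one of them turns on whether a CR was genuine. The SAP names no person, eCRF field or query to settle that. A program that follows the PR bullet literally would count as a responder someone whom footnote a treats as having progressed.

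Confirmed response is the ORR numerator and the entry condition for TTR and DOR (SAP 7.3, 7.4). It also counts towards CBR (SAP 7.2), and a scan re-read as PD is a PFS event (SAP 7.5). Anti-tumour activity is one input to choosing the recommended Phase 2 dose, where only 6-12 subjects are planned.

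**Working it through.** **Plan figures reproduced.** Total N: 21 + 6 + 6 = 33 and 42 + 6 + 6 = 54, as in SAP 3.3. SD minimum: 8 × 7 − 7 = 49 days, as in SAP 7.1.

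**Conflict 1: CR then PR, at least 4 weeks apart.**

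| Source | Result |
|---|---|
| PR bullet on recorded responses | confirmed PR |
| Footnote a, CR real | second scan is PD; best response SD (PD if the 49-day minimum is unmet) |
| Footnote a, CR corrected to PR | PR |

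If the second scan is re-entered as PD, the bullet's condition that both determinations precede progression also excludes it, and the rules agree. Nothing in SAP 7.1 tells the program or the site to make that change.

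Effect on CBR: with CR at week 8 and PR at week 16, a confirmed PR counts, while CR/PR followed by PD is a No in the SAP 7.2 table. With SD at week 8, CR at week 16 and PR at week 24, the SD ≥ 16 weeks row already gives Yes, so CBR does not move.

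**Conflict 2: PR or CR then SD, minimum unmet, no PD documented.** Table 3 gives PD. The PD bullet cannot apply without documented PD, and the NE bullet gives NE. For the minimum to be unmet, both scans must fall before day 49. The first scheduled scan is at week 8, so this takes two early scans. Neither PD nor NE is a response, so ORR is unaffected.

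**How often the rules part.** Both rules were coded over all three-visit sequences of CR, PR, SD, PD and NE, stopped at recorded PD, with the first scan at week 8. Assumption: Table 3 pairs are combined by the SAP's ranking. Number of sequences whose responder status differs from the bullets:

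| Reading of the subsequent time point | CR corrected to PR | CR real |
|---|---|---|
| any later scan | 0 | 7 |
| next scan only | 8 | 13 |

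The 7 all contain a CR followed later by a PR. The 8 all have SD or NE between two responses, including PR-SD-PR and PR-NE-PR. The two sets share CR-SD-PR and CR-NE-PR: 7 + 8 − 2 = 13. If the scan re-read as PD also ends the response window, CR-PR-PR and CR-PR-CR join the right-hand column, giving 7 + 2 = 9 and 13 + 2 = 15. These count patterns; they are not probabilities.

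**Size of one reclassified subject (100/n).** n=6: 16.7 points; n=12: 8.3; n=33: 3.0; n=54: 1.9. With exact 95% intervals and illustrative counts: 0/6 = 0% (0-45.9) against 1/6 = 16.7% (0.4-64.1); 0/12 = 0% (0-26.5) against 1/12 = 8.3% (0.2-38.5); 1/33 = 3.0% (0.1-15.8) against 2/33 = 6.1% (0.7-20.2).

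**The case against.** The best defence is that footnote a already resolves CR-then-PR. A real CR makes the second scan PD, which the bullet then excludes; a mis-called CR is changed to PR, which the bullet then confirms. On this view the correction belongs in the investigator's data and the program only reads the result. That is a fair account of the intent. It does not cover a CR-PR pair left uncorrected, which the bullet counts as a response and footnote a may not.

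On the second conflict, one bullet sends the reader to the table when the SD minimum is unmet, so Table 3 might be said to govern there. But that bullet makes the result depend on later assessments, and Table 3 would still assign PD to a subject with none documented, against the PD and NE bullets. The objection that this is rare stands.

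A reader might also infer that Table 3 makes PR-SD-PR and PR-NE-PR stable disease. The documents do not say so. Those sequences become SD only if the subsequent time point means the very next scan. Read as any later scan, the PR-PR row agrees with the bullet, and that reading fits Protocol 16.5.2 (confirmation in a subsequent scan) and SAP 7.4 (confirmation at least 28 days later). These cases are ambiguous, not contradictory.

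Finally, ORR is a secondary endpoint with no hypothesis test, the Phase 2 dose rests on all the data, and listings and spider plots show each subject's course. All of that limits the consequence.

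**Conclusion.** Two conflicts are real as written. Recorded CR then PR is confirmed PR under the bullet and SD, PD or PR under Table 3, depending on an unassigned judgement. It can alter ORR, TTR and DOR membership and PFS, and can alter CBR when the CR is at the first scan. PR or CR then SD with the minimum unmet is PD under Table 3 and NE under the bullets when no PD is documented; it touches only the best-response table. Non-adjacent confirmation needs a clarifying sentence and no more.

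The size is 16.7, 8.3 or 3.0 ORR points per affected subject at n=6, 12 or 33. The documents give no basis for forecasting how many subjects will be affected, so no expected number is offered. The conclusion assumes that the program works from the recorded time-point responses, as SAP 7.1 describes. This is a low-impact correction, worth making because specific wording removes it.

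**What to change.** Amend SAP 7.1 before database freeze:

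1. Query every recorded CR followed by PR. If the investigator upholds the CR, the later scan is entered as PD, as footnote a provides, and carries through to best response, DOR and PFS. If the CR is corrected to PR, the PR bullet gives confirmed PR. The program must not count an unresolved CR-PR pair as a confirmed PR.
2. In the PR-then-SD and CR-then-SD rows of Table 3, change the fallback from PD to NE unless PD is later documented.
3. State that confirmation may come from any later assessment at least 4 weeks away and before progression, with intervening SD or NE allowed, in line with Protocol 16.5.2 and SAP 7.4.

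The cost is a few sentences, matching program logic and a small number of site queries. No new assessments or data are needed.

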7.2 Clinical Benefit Rate

The CBR based on RECIST 1.1 is defined as the proportion of subjects whose best overall response is a confirmed CR, confirmed PR or SD \geq 16 weeks, where SD \geq 16 weeks is defined as at least one SD or better for \geq 15 weeks (16 weeks with 1 week visit window) and not qualifying for a confirmed CR or PR as the following:

Response at week 8 assessment	Response at week 16 assessment	Response at week 24 assessment	SD ≥ 16 weeks
SD	SD/PR/CR	Any	Yes
SD	PD	Any	No
SD	NE/missing	SD/PR/CR	Yes
SD	NE/missing	PD/NE/missing	No
CR/PR	PD	Any	No
PR	SD	Any	Yes
NE	SD	Any	Yes

The CBR will be estimated with a 95% CI using the exact probability method. Summary of CBR will be provided for the All Treated population and Response Evaluable population.

NE = not evaluable.

^a If a CR is truly met at first time point, then any disease seen at a subsequent time point, even disease meeting PR criteria relative to baseline, makes the disease PD at that point (since disease must have reappeared after CR). Best response would depend on whether minimum duration for SD was met. However, sometimes "CR" may be claimed when subsequent scans suggest small lesions were likely still present and in fact the patient had PR, not CR at the first time point. Under these circumstances, the original CR should be changed to PR and the best response is PR.

7.3 Time to Response

The TTR based on RECIST 1.1 is defined as the time from the first dose until the first documentation of a subsequently confirmed objective response (confirmed CR or confirmed PR). Only subjects who have achieved confirmed objective response will be evaluated for TTR, and individual TTR will be presented in a data listing. If data warrants, TTR will be summarized descriptively and graphically using Kaplan-Meier methods. The Kaplan-Meier estimate for the median TTR along with 95% confidence intervals and the first and third quartiles will be determined. Brookmeyer-Crowley method will be used for the confidence interval calculation. Kaplan-Meier estimate of TTR rate at 8 weeks, 16 weeks, and other timepoints of interest will be included in the summary table.

7.4 Duration of Response

The DOR based on RECIST 1.1 is defined as the time from the date of the first CR or PR (confirmed at least 28 days later) to the date of first documented disease progression per RECIST 1.1 or death, whichever occurs first. Only subjects who have achieved a confirmed CR or confirmed PR will be evaluated for DOR, and individual DOR will be presented in a data listing.

If a disease progression does not occur, DOR will be censored as of the date of the last evaluable disease assessment. The evaluable disease assessment is defined as an assessment for which the overall response can be determined. The censoring guidance and the date of PD/death or censoring are same as those for PFS in Section 7.5. If data warrants, DOR will be summarized descriptively and graphically using Kaplan-Meier methods. The Kaplan-Meier estimate for the median DOR along with 95% confidence intervals and the first and third quartiles will be determined. Brookmeyer-Crowley method will be used for the confidence interval calculation. Kaplan-Meier estimate of DOR rate at 8 weeks, 16 weeks, and other timepoints of interest will be included in the summary table.

7.5 Progression Free Survival

The PFS based on RECIST 1.1 is defined as time from the first day of treatment to the first documented disease progression per RECIST 1.1 or death from any cause, whichever occurs first. Subjects who have not progressed at the time of analysis will be censored at the date of their last evaluable disease assessment. Subjects who start new anticancer therapy prior to the documented PD will be censored at the last evaluable disease assessment prior to the start of new anticancer therapy. The censoring guidance and the date of PD/death or censoring are given in the Table 4 below.

Table 4. Summary of Censoring Guidelines for PFS based on RECIST1.1

Situation	Date of PD/Death or Censoring	PFS Outcome
Documented PD or death from any cause	Date of the PD or death, whichever comes first	Event (unless the censoring rule specified below)
Start new anticancer therapy before documented PD	Date of last evaluable disease assessment prior to the start of new anticancer therapy	Censored
Death or PD immediately after ≥ 2 consecutive missed or non-evaluable disease assessments ¹ as per the protocol specified assessment schedule	Date of last evaluable disease assessment prior to missed or non-evaluable assessments, or the first dose of investigational product, whichever occurred last	Censored
No PD or death at time of analysis or lost to follow-up	Date of last evaluable post-baseline disease assessment	Censored
(No baseline disease assessment OR no post-baseline disease assessment) AND no death	Date of first dose with a duration of 1 day	Censored

¹ Two or more consecutive disease assessments is defined as \geq 16+1 weeks for the first 6 months or \geq 24+1 weeks for 6-24 months (two disease assessments as per protocol plus a one week visit window) after the last evaluable post-baseline disease assessment. If a subject has two or more consecutive missed or non-evaluable assessments followed by an assessment showing no radiologic disease progression, then the assumption will be that the subject did not progress during the missed or non-evaluable assessments.

If data warrants, PFS will be summarized descriptively and graphically using Kaplan-Meier methods. The Kaplan-Meier estimate for the median PFS along with approximate 95% confidence intervals and the first and third quartiles will be determined. Brookmeyer-Crowley method will be used for the confidence interval calculation. Kaplan-Meier estimate of PFS rate at 8 weeks, 16 weeks, 24 weeks, 48 weeks, and other timepoints of interest will be included in the summary table. PFS will be summarized and listed for the All Treated population.

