5.2 Reporting Conventions

The statistical analyses will be reported using summary tables, figures, and data listings. The International Conference on Harmonisation (ICH) numbering convention will be used for tables, listings, and figures.

Data from all participating sites will be pooled prior to data summary or analysis. It is anticipated that subject accrual will be spread thinly across sites and summaries of data by site will not be informative and therefore, will not be provided.

Unless specified otherwise, all summary tables will be presented by dose schedule/level for all subjects in the analysis population, and subjects from dose escalation, pharmacodynamic and dose expansion cohorts will be pooled. Summaries will also be provided for subjects at the same dose level pooled across schedules. Select safety summary tables may be provided for the dose escalation cohorts.

All individual subject data listings will be presented by dose level, dose schedule and subject, unless specified otherwise. Data from all assessments, whether scheduled or unscheduled, will be included in the listings. Listings will present the data in their original format (without any imputation), unless specified otherwise.

Summaries by planned time point will include data from scheduled assessments and all data will be reported according to the nominal visit for which it will be recorded (i.e., no visit windows will be applied). Unscheduled data, when summarized, will be included only in calculation of the maximum or minimum value over time such as worst-case post-baseline. If multiple assessments are reported on the same date for the same scheduled planned time, the worst-case result will be analyzed.

Continuous variables will be summarized with means, standard deviations, medians, minimums, and maximums. The precision of the original measurements will be maintained in summaries and listings, when possible. Generally, means and medians will be presented to one more decimal place than the raw data, and the standard deviations will be presented to two more decimal places than the raw data.

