5.3.3 Study Day, Duration, and Time from Event

The reference date for age calculation is the date of consent form signed as age is an eligibility requirement. The reference date for safety, efficacy and other data analyses is the date of the first dose.

• Study Day – Study Day 1 is defined as the date of the first dose; the day before the first dose is defined as Study Day -1. There is no study day 0. For a given event date, Study Day is calculated relative to the date of first dose of study drug.

```
Study Day = [Event Date – First Dose Date] (in days) + 1 day, where the event date is on or after the first dose date.

Study Day = [Event Date – First Dose Date] (in days), where the event date is before the first dose date.
```

• **Duration (Days)** – A duration is calculated as the stop date minus the start date plus one.

```
Duration (days) = [Stop Date - Start Date] (in days) + 1 day.
```

- **Time since an event** -Time since an event (e.g. time since initial diagnosis) is calculated as the reference date minus the event date. For time since initial diagnosis, the reference date is the first dose of study treatment.
- **Time to an event-** Time to an event (e.g. time to response, PFS, OS) is calculated as the event date minus the reference date+1. For time to response, PFS and OS, the first dose of study treatment is the reference date.

To convert days to months, divide the number of days by 30.4375 (365.24/12) and round to one decimal place.

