7. EFFICACY ANALYSES

The efficacy endpoints include ORR, CBR, TTR, DOR, PFS, and OS. The efficacy endpoints ORR, CBR, TTR, DOR, and PFS will be based on the investigator disease assessment per RECIST 1.1. Exploratory analyses of these endpoints will be based on the investigator disease assessment per iRECIST (iORR, iCBR, iTTR, iDOR and iPFS).

The efficacy analyses will be based on the All Treated population and/or Response Evaluable population, as appropriate. Subjects who do not have any post-baseline disease assessment will be considered as non-responders in the calculation of response rate.

Disease response will be evaluated and documented in CRF based on RECIST 1.1 until the first PD per RECIST 1.1, and then will be evaluated and documented in CRF based on iRECIST. Disease assessment will be performed at baseline (screening visit) and at the following intervals until disease progression: every 8 weeks until week 24 and every 12 weeks thereafter until year 2 and every 6 months until study conclusion. Confirmatory scans should be performed at least 4 weeks (>28 days) after initial documentation of an objective response. If subjects discontinue study treatment prior to progressive disease, they should continue to be followed with radiologic disease assessments until disease progression, start of a new anti-cancer therapy, withdrawal of consent or death, whichever is earliest.

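### SAP Table 4 footnote 1: the 17- and 25-week limits for two missed scans do not fit the change of scan interval at week 24, and the date that selects the limit is not stated, so PFS and DOR outcomes can be misclassified

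*SAP*

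**What the plan says.** - **Schedule.** SAP 7 sets disease assessments "every 8 weeks until week 24 and every 12 weeks thereafter until year 2". Protocol 6.8 and 8.1 give the same switch at week 24.
- **Censoring row.** SAP 7.5, Table 4, censors PD or death that comes immediately after two or more "consecutive missed or non-evaluable disease assessments", judged against the protocol schedule. The censoring date is the last evaluable scan before the gap "or the first dose of investigational product, whichever occurred last".
- **Footnote 1.** It defines two or more consecutive assessments as a gap of at least 16+1 weeks in the first 6 months, or at least 24+1 weeks from 6 to 24 months. Its explanation is "two disease assessments as per protocol plus a one week visit window) after the last evaluable post-baseline disease assessment". It fixes where the gap starts. It does not say whether the date of that scan or the date of PD or death decides which period applies, and it gives no limit after 24 months.
- **DOR.** SAP 7.4: "The censoring guidance and the date of PD/death or censoring are same as those for PFS".

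**The concern.** The two limits are twice the 8-week interval plus one week and twice the 12-week interval plus one week. They can be right only when both missed scans lie on the same interval. After a last evaluable scan at week 16 the next two scans are weeks 24 and 36, one on each interval, and neither limit fits. The missing statement of which date selects the period adds a second problem: two programmers following the text could code the same subject differently.

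At stake is whether an observed PD or death counts as an event or is censored back to an earlier scan. DOR is a secondary outcome and PFS an exploratory one. Individual values of both are listed even if no Kaplan-Meier summary is made.

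**Working it through.** **Inputs**
- Scan weeks 8, 16, 24, 36, 48, 60 (SAP 7; Protocol 6.8 and 8.1). Check: the tumor-assessment footnote in Protocol 6.1 puts the first 12-weekly scan before cycle 10, and with 28-day cycles (10 - 1) x 4 = week 36.
- Visit window +/-7 days (Protocol 6.1, footnote b). Scans follow the calendar and do not move with dose delays (Protocol 8).
- Six months, from SAP 5.3.3 ("To convert days to months, divide the number of days by 30.4375"): 6 x 30.4375 = 182.6 days = week 26.1. Week 24 (day 168) is therefore in the first 6 months.
- Days are counted from first dose, with week w taken as day 7w.

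**1. The plan's own figures.** 2 x 8 + 1 = 17 and 2 x 12 + 1 = 25. Both reproduce.

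**2. The same definition at each scan.** Required gap = week of the second following scan + 1 - week of the last evaluable scan.

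| Last evaluable scan | Next two scans | Required gap (weeks) | Limit if last scan selects | Limit if event selects (event after week 26.1) |
|---|---|---|---|---|
| 8 | 16, 24 | 24 + 1 - 8 = 17 | 17 | 25 |
| 16 | 24, 36 | 36 + 1 - 16 = 21 | 17 | 25 |
| 24 | 36, 48 | 48 + 1 - 24 = 25 | 17 | 25 |
| 36 | 48, 60 | 60 + 1 - 36 = 25 | 25 | 25 |

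**3. If the last scan selects the period (too much censoring)**
- Last scan week 16: the limit is reached on day 112 + 119 = 231 (week 33). The week-36 window closes on day 252 + 7 = 259 (week 37). PD or death in weeks 33-37 is censored although two scans have not been missed. PD on the on-time week-36 scan, with only week 24 missed, has a gap of 20 weeks and is censored to week 16. With both scans anywhere in their windows the gap is 140 +/- 14 = 126 to 154 days, always above 119.
- Last scan week 24: the limit is reached on day 168 + 119 = 287 (week 41). The week-48 window closes on day 336 + 7 = 343 (week 49). PD at week 48 with only week 36 missed (gap 24 weeks) is censored.

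**4. If the event selects the period (too little censoring).** PD on a nominally timed scheduled scan is classified correctly. Death or unscheduled PD after two missed scans may not be:
- Last scan week 8: the week-24 window closes on day 175, but after day 182.6 the limit is 25 weeks, reached on day 56 + 175 = 231. Days 183-230 (weeks 26.1-32.9) count as events.
- Last scan week 16: the week-36 window closes on day 259, but the limit is reached on day 112 + 175 = 287. Days 260-286 (weeks 37.1-40.9) count as events.

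**5. Size for one subject, last-scan reading.** PR at week 8, confirmed at week 16, week 24 missed, PD at week 36. For DOR, SAP 5.3.3 states: "A duration is calculated as the stop date minus the start date plus one".
- DOR: censored at 112 - 56 + 1 = 57 days (1.9 months) instead of an event at 252 - 56 + 1 = 197 days (6.5 months).
- PFS: censored at 112 + 1 = 113 days (3.7 months) instead of an event at 252 + 1 = 253 days (8.3 months).

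**6. Fixed gaps and visit windows.** Even on one interval, a gap counted between actual dates can exceed the limit after one missed scan: 112 +/- 14 = 98 to 126 days against 119, and 168 +/- 14 = 154 to 182 days against 175. In each case 36 of the 15 x 15 = 225 possible date pairs do so. This counts date pairs and is not a probability.

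**The case against.** The strongest defence is that the Table 4 row governs, and that the footnote's explanation applied to week 16 already gives 21 weeks. On that view the defect is two incomplete numbers beside a correct definition. It stands in part: the intent is recoverable. It does not rescue the text, because the footnote presents the two gaps as the definition, and using 21 means overriding a printed limit.

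The consequence is also modest, and this stands:
- An affected case needs missed or non-evaluable scans and an event in particular weeks. Protocol 3.11 requires sites to try to reschedule missed visits.
- DOR covers confirmed responders only. If the rate the protocol cites for another anti-CD47 antibody in ovarian cancer (2 of 13) applied here, 33 to 54 subjects would give about 5 to 8 responders.
- Kaplan-Meier summaries are made only if the data warrant. Tumor responses are listed, so a reader could reclassify a case.
- The two readings do not both fail on the scheduled-scan example. With the event date selecting, that subject is classified correctly.

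A reader might go further and infer that events in this trial are in fact misclassified, or that the reported medians are biased by a knowable amount. The documents do not support this. They give no count of missed scans and do not show which reading was programmed.

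**Conclusion.** The footnote is wrong as written. It has no limit that fits a last scan at week 16, and it leaves open which date selects the limit. Each choice contradicts the Table 4 row for some subjects: the last-scan choice after week 16 or week 24, the event-date choice after week 8 or week 16. PFS and DOR outcomes can be misclassified, in either direction. For one subject the shift can be large (DOR 57 days censored against 197 days with an event). Across the trial it is likely to touch few subjects, and the number cannot be derived from the documents.

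The result assumes nominal scan dates except where windows are shown, and the SAP's own month conversion. The week-16 problem does not depend on exactly where 6 months falls. MTD decisions rest on DLTs and are untouched.

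**What to change.** Replace the fixed gaps with a visit count, for both PFS and DOR:

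- The nominal visit of the last evaluable scan decides. Censor at that scan only if PD or death occurs later than 7 days after the scheduled date of the second consecutive scheduled scan missed or non-evaluable since then. Otherwise count the event.
- PD found on a scheduled scan counts at that scan's nominal visit. An unscheduled or confirmatory scan is placed between the nominal visits on either side of it.
- With no evaluable post-baseline scan, start the count at first dose, a date the Table 4 row already names.

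On nominal dates this gives 17 weeks from week 8, 21 from week 16, and 25 from week 24 or later in the 12-week phase. If a shorter text is wanted, one sentence giving those three limits by scheduled week of the last scan carries the main correction.

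The nominal-visit assignment matters. If visits were counted by date alone, a scan done 1 to 7 days early would leave its own visit looking missed, and 7 x 15 = 105 of the 225 date pairs would be wrong. SAP 5.2 already says "all data will be reported according to the nominal visit for which it will be recorded (i.e., no visit windows will be applied". That sentence concerns summaries by planned time point, so the time-to-event rule needs its own statement.

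One effect should be stated openly. After a confirmatory scan at week 12, missing weeks 16 and 24 leads to censoring of events after week 25, a gap of 25 - 12 = 13 weeks. This follows the Table 4 row but is shorter than 17.

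After year 2, reconcile the schedule before applying the count. Protocol 6.8 says every 24 weeks, while Protocol 8.1 and SAP 7 say every 6 months. The Protocol 6.1 footnote lists cycles 28 and 31 (weeks 27 x 4 = 108 and 30 x 4 = 120) as up to year 2.

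The cost is SAP wording and programming. A few PFS or DOR outcomes may change, in either direction.
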